3.2 Primary Study Endpoints

Primary Objective:

To evaluate the safety and tolerability of using platelet rich plasma on the NVB after nervesparing radical prostatectomy.

3.3 Secondary Study Endpoints

Secondary Objective(s):

- To assess the feasibility of applying 1 dose of PRP intra-operatively at the time of bilateral nerve-sparing RP in 20 men with prostatic adenocarcinoma.
- To assess preliminary clinical benefit/efficacy of using PRP in facilitating early nerve healing and decreasing ED at 3, 6, 9, 12 and 18 months after nerve-sparing RP.
- To assess change in urological function by measuring urinary continence before and at 3, 6, 9, 12 and 18 months after PRP treatment during nerve sparing surgery.

4 Subject Selection Enrollment and Withdrawal

4.1 Inclusion Criteria

The study involves men newly diagnosed with prostatic adenocarcinoma that are selecting RP for treatment. The men identified for the study would be from the outpatient clinic setting and all men would be able to give appropriate informed consent.

The following are inclusion criteria for the study:

- Newly diagnosed, clinically localized prostatic adenocarcinoma
- Age 50 60 years
- Male gender
- Normal preoperative sexual function (as defined by Sexual Health Inventory for Men questionnaire score > 19; see attachment)

• Normal urinary continence (as defined by Expanded Prostate Cancer Index Composite, question 5, response = none, see attachment)Regular sexual partner

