3.1 General Design

This is an open label, human study evaluating the safety and tolerability, feasibility, and efficacy, s of PRP applied in topical fashion intra-operatively during RP. Subjects will be screened at outpatient clinic visit appointments and interested qualified subjects will be

consented and offered participation in this trial. The study aims to enroll 20 men with newly diagnosed prostatic adenocarcinoma that are planning to undergo bilateral nerve-sparing RP. Once written consent has been obtained baseline functional and laboratory assessments will be obtained and patients will be followed for the expected duration for study participation of 18 months.

Since the present study is a single-arm study, evaluation of safety and efficacy parameters will have to be performed using benchmark outcomes from historical controls. At Mayo Clinic, all patients undergoing RP are included in the Mayo Clinic Prostatectomy Registry. The prostatectomy registry is prospectively maintained by study nurses. The prostatectomy registry maintains detailed oncologic and quality of life data using PSA testing and the same validated questionnaires proposed by the current study. The comparator for the present study would be other subjects from the Mayo Clinic Prostatectomy Registry that underwent bilateral nervesparing RP within the same study dates and met all of the other inclusion and exclusion criteria for the present study but did not have PRP applied intraoperatively to the neurovascular bundles.

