4.2 Exclusion Criteria

- Unable or unwilling to provide informed consent
- Vulnerable study populations
- Active systemic infection
- Diabetes Mellitus diagnosis
- Preexisting ED or urinary incontinence
- Metastatic or locally advanced prostatic adenocarcinoma on preoperative evaluation
- Men found grossly or pathologically to have locally advanced or metastatic disease at the time of RP
- An estimated blood loss of >750 mL at the time of RP
- Treatment prior to surgery with any form of hormones, antiandrogens or androgen deprivation therapy
- Use of an antidepressant, beta blocker or ED medication at the time of study
- Screening Men without a regular sexual partner
- Use of aspirin or heparin 2 weeks before RP
- Need for use of aspirin or heparin for 2 weeks or more after RP.

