4.4 Early Withdrawal of Subjects

4.4.1 When and How to Withdraw Subjects

A subject may withdraw at any time prior to RP. There are no adverse safety considerations in the study for those deciding to withdraw from the study. Subjects may choose to discontinue study participation after RP surgery and will be counted as withdrawn

A subject consenting to the study will receive PRP at the time of RP unless the surgical team decides intra-operatively to withdraw a subject from the study in the following situations:

- Estimated blood loss greater than 750 mL
- Evidence of disease grossly and/or pathologically that the prostate cancer is locally advanced or metastatic

• Documentation of the reason for withdrawal will be retained in the study files.

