8.6 Medical Monitoring

It is the responsibility of the PI to oversee the safety of the study at his/her site. This safety monitoring will include careful assessment and appropriate reporting of adverse events as noted above, as well as the construction and implementation of a site data and safety-monitoring plan (see section 10 "Study Monitoring, Auditing, and Inspecting"). Medical monitoring will include a regular assessment of the number and type of serious adverse events.

Since the present study is a single-arm study, evaluation of safety and efficacy parameters will also be performed using benchmark outcomes from historical controls. At Mayo Clinic, all patients undergoing RP are included in the Mayo Clinic Prostatectomy Registry. The prostatectomy registry is prospectively maintained by study nurses. The prostatectomy registry maintains detailed oncologic and quality of life data using PSA testing and using the same validated questionnaires proposed by the current study. By using other subjects from the Mayo Clinic Prostatectomy Registry that underwent bilateral nerve-sparing RP within the same study dates (and those that met all of the other inclusion and exclusion criteria for the present study but did not have PRP applied intraoperatively to the neurovascular bundles), another means to compare the safety and preliminary evidence of efficacy will be achieved.

9 Data Handling and Record Keeping

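### Registry controls are defined by bilateral nerve-sparing performed and trial men by bilateral nerve-sparing planned, so the erectile-function benchmark can be biased against PRP if any analysed man loses a bundle

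*Combined protocol and SAP*

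**What the plan says.** **Trial men.** Section 3.1 aims to enrol men "that are planning to undergo bilateral nerve-sparing RP". Section 4.1 turns the target population into a list of criteria, beginning with "Newly diagnosed, clinically localized prostatic adenocarcinoma". No item in it mentions nerve-sparing, planned or performed.

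**Exclusions and withdrawal at surgery.** Section 4.2 lists two findings at operation. One is blood loss above 750 mL. The other is "Men found grossly or pathologically to have locally advanced or metastatic disease at the time of RP". Section 4.4.1 uses the same two as reasons to withhold PRP: "A subject consenting to the study will receive PRP at the time of RP unless the surgical team decides intra-operatively to withdraw a subject" for one of them. Loss of a bundle is not a reason.

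**Analysis population.** Section 7.3 takes men who consented and went on to complete postoperative visits, with no condition on nerve-sparing.

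**Registry controls.** Section 3.1 defines the comparator as registry men who "underwent bilateral nervesparing RP within the same study dates and met all of the other inclusion and exclusion criteria". Section 8.6 repeats this: men "that underwent bilateral nerve-sparing RP within the same study dates".

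**Recording.** Neither the surgery visit (Section 6.2) nor the schedule of events (Section 6.8) lists the nerve-sparing achieved as an item to collect.

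**The concern.** The trial has one arm, and Section 3.1 makes the registry the yardstick for both safety and efficacy. The benchmark is informative only if the two groups are assembled by the same rule. Here one group is defined by intention before surgery and the other by what the surgeon accomplished.

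Suppose a man planned for bilateral sparing ends with one bundle preserved, for a reason other than advanced disease or blood loss. In the trial he receives PRP and is analysed. In the registry he fails the control definition and drops out. The protocol's own rationale (Section 1.1) is that erectile recovery may depend on the bundle tissue left behind, so such men would be expected to recover less often. The PRP group could then look worse than its benchmark for a reason unrelated to PRP. Without recorded nerve-sparing status, a reader could neither see nor adjust for this.

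**Working it through.** **1. Is there a rule that closes the gap?** For a man who loses a bundle for a reason other than the two listed operative findings:

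- Entry list (4.1): silent, so he qualifies.
- Exclusions (4.2): not excluded.
- Withdrawal at surgery (4.4.1): not withdrawn, so PRP is given.
- Analysis population (7.3): included if he completes his visits.
- Registry control definition (3.1, 8.6): the corresponding man is left out.

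The mismatch therefore stands in the text as written.

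**2. Is there a stated figure to reproduce?** No. Section 7.1 gives n=20 without an error rate, power, effect size or control rate. The documents give neither the share of men who lose a bundle nor the recovery difference. The sizes below are illustrations.

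**3. Size of this component.** Assume no true PRP effect. Let f be the share of analysed PRP men without bilateral sparing, and d the difference in recovery (SHIM above 19, Section 7.2) between men with and without it. All controls have bilateral sparing, so

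bias = −f × d.

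The main assumption is d = 20 to 30 percentage points; 10 to 40 is shown as a wider range.

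| f | men of 20 | bias, d = 20 to 30 | bias, d = 10 to 40 |
|---|---|---|---|
| 0% | 0 | 0 | 0 |
| 5% | 1 | −1 to −1.5 points | −0.5 to −2 points |
| 10% | 2 | −2 to −3 points | −1 to −4 points |
| 20% | 4 | −4 to −6 points | −2 to −8 points |

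For example, 0.10 × 20 = 2 and 0.10 × 30 = 3.

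**4. How likely is at least one such man?** If each man independently has probability f of losing a bundle, the chance of at least one among 20 is 1 − (1 − f)^20. This is 64% at 5%, 88% at 10% and 99% at 20%.

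**5. Comparison with sampling error.** For 10 recoveries in 20, the exact (Clopper-Pearson) 95% interval is 27% to 73%, about 23 points either way. Every value in the table is well inside that.

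**6. A bias that could run the other way.** Sections 4.4.2 and 4.4.3 discard and replace withdrawn men, and Section 7.3 analyses those who complete visits. If a share g is dropped and completers recover more often than dropouts by e, the completer mean exceeds the mean of all treated men by g × e. With g = 10% and e = 10 to 30 points (both assumed), that is +1 to +3 points, similar in size to the 10% row above.

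**The case against.** The strongest reply is that the intent is plain. The feasibility objective (Sections 2 and 3.3) concerns bilateral nerve-sparing surgery in 20 men. Section 3.1 asks controls to meet all the *other* criteria, which treats bilateral sparing as a criterion already. On that reading, a shared requirement was simply left off the list in 4.1. This is fair, and nothing suggests the groups were deliberately set up differently. But adding the missing item as Section 3.1 words it would still leave planned on one side and performed on the other.

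The exclusion of men found to have advanced disease at surgery applies to both groups and may already remove some men whose bundle was sacrificed. That stands: it lowers the plausible share, though it does not cover other reasons for losing a bundle.

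The consequence is also limited. The primary objective is safety and tolerability, efficacy is secondary and preliminary, and Section 7.2 is descriptive with no test or estimator for the registry comparison. This bears on severity. A descriptive benchmark still needs like-for-like groups.

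Finally, selecting controls on bilateral sparing presupposes that the registry can supply that status, and Section 3.1 says all the institution's prostatectomy patients are in it. Trial men's status is therefore probably retrievable, which makes the fix cheap but does not make it unnecessary.

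**Conclusion.** The mismatch is real: controls are selected on performed bilateral sparing, trial men on planned, and no entry, withdrawal or analysis rule reconciles the two. If at least one analysed PRP man lacks bilateral sparing and such men recover less often, this component of the erectile comparison is biased against PRP. With an assumed gap of 20 to 30 points, the size runs from 0 if no man loses a bundle to 4 to 6 points at 20%. These are illustrations, not estimates from the documents, and they are small beside the sampling error at n=20.

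A reader might infer that the comparison as a whole is biased against PRP. The documents do not support that. They do not show that any treated man will lack bilateral sparing, and the completer-only analysis could favour PRP by a similar amount, so the net direction is not established. An opposing bias of unknown size is no correction, however, and the definitions should still be aligned.

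**What to change.** - **Section 4.1:** list planned bilateral nerve-sparing as an inclusion criterion, to match 3.1.
- **Case report form:** record the nerve-sparing achieved on each side, taken from the operative note.
- **Sections 3.1, 7.3 and 8.6:** state that the efficacy comparison with the registry uses the same basis in both groups. Performed bilateral sparing in both is the simpler choice, because controls are already selected that way. It also conditions on something the product cannot have altered, since Section 5.4.1 places PRP application after the anastomosis. Planned in both is the alternative, if the registry holds that information.
- **Safety:** keep every PRP-treated man in the safety analysis whatever his nerve-sparing status, and report separately the outcomes of treated men without bilateral sparing.

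If both groups are restricted to performed bilateral sparing, f = 0 and this bias component is zero.

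The cost is one inclusion line, one form item per side and a sentence in each of three sections. No treatment rule changes and patients have no added burden. The downside is that the efficacy comparison may include slightly fewer than 20 men; for example, 18 if two lose a bundle.

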4.2 Exclusion Criteria

- Unable or unwilling to provide informed consent
- Vulnerable study populations
- Active systemic infection
- Diabetes Mellitus diagnosis
- Preexisting ED or urinary incontinence
- Metastatic or locally advanced prostatic adenocarcinoma on preoperative evaluation
- Men found grossly or pathologically to have locally advanced or metastatic disease at the time of RP
- An estimated blood loss of >750 mL at the time of RP
- Treatment prior to surgery with any form of hormones, antiandrogens or androgen deprivation therapy
- Use of an antidepressant, beta blocker or ED medication at the time of study
- Screening Men without a regular sexual partner
- Use of aspirin or heparin 2 weeks before RP
- Need for use of aspirin or heparin for 2 weeks or more after RP.

4.3 Subject Recruitment, Enrollment and Screening

Subjects will be recruited for the study in the outpatient clinic environment by the PI and Co-Investigators. Identified subjects will discuss the study with a Study Coordinator. At that time, the inclusion and exclusion criteria will be discussed as well as the rationale, the potential benefits, and potential risks associated with the study. The recruitment, enrollment, and screening procedures will occur in the outpatient clinic setting. If subjects want to proceed with the study, informed consent will be obtained by the study coordinator or investigator.

4.4 Early Withdrawal of Subjects

4.4.1 When and How to Withdraw Subjects

A subject may withdraw at any time prior to RP. There are no adverse safety considerations in the study for those deciding to withdraw from the study. Subjects may choose to discontinue study participation after RP surgery and will be counted as withdrawn

A subject consenting to the study will receive PRP at the time of RP unless the surgical team decides intra-operatively to withdraw a subject from the study in the following situations:

- Estimated blood loss greater than 750 mL
- Evidence of disease grossly and/or pathologically that the prostate cancer is locally advanced or metastatic

• Documentation of the reason for withdrawal will be retained in the study files.

4.4.2 Data Collection and Follow-up for Withdrawn Subjects

As part of normal clinical care, subjects that have withdrawn from the study will still have routine postoperative monitoring after RP. Any collected study data from withdrawn subjects will not be included in the data analysis. Since all patients have their outcomes tracked after RP at Mayo Clinic, postoperative data would be available should this be needed as part of another study protocol.

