PI Principal Investigator
PRP Platelet rich plasma
RP Radical Prostatectomy

PSA Prostate-Specific Antigen

SAE Serious Adverse Event/Serious Adverse Experience

SHIM Sexual Health Inventory for Men SOP Standard Operating Procedure

Study Summary

Title	A Study Evaluating Intraoperative Application of Platelet-Rich Plasma to the Neurovascular Bundles During Nerve-Sparing Radical Prostatectomy: Initial Technical Description and Prospective Early Postoperative Outcomes Analysis					
Running Title	PRP Application During RP					
Protocol Number	16-001320					
Methodology	Open label					
Overall Study Duration	18 months					
Subject Participation Duration	18 months					
Single or Multi-Site	Single site					
Objectives	To evaluate the safety, tolerability, feasibility and efficacy of using platelet rich plasma to facilitate early nerve healing and decrease erectile dysfunction after nerve-sparing radical prostatectomy.					
Number of Subjects	20					
Diagnosis and Main Inclusion Criteria	Post-surgical erectile and urinary dysfunction. Main inclusion criteria are men, aged 50-60 years, with normal sexual function and regular sexual partner, undergoing RP for newly diagnosed prostatic adenocarcinoma.					
Study Product, Dose, Route, Regimen	Autologous Platelet-Rich Plasma The dose is approximately 1,000,000 platelets/mL and the product is applied topically to the neurovascular bundle once during radical prostatectomy					
Duration of Administration	One time drug administration with duration of drug application is approximately 4 hours.					
Reference therapy	None					
Statistical Methodology	The safety evaluation will focus on the number of adverse events including local reactions, expected serious adverse events and unexpected serious adverse events. All events will be collected, recorded and assessed for severity as a means to facilitate the reporting process. All patients will undergo an assessment of sexual and urinary function and oncologic outcomes at 3, 6, 9, 12 and 18 months after surgery. All patients will be evaluated for perioperative complications, length of stay, and need for blood transfusion.					

Version 4.0

1 Introduction

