Platelets contain growth factors and the hypothesis of the study is that the growth factors will augment healing of the NVB after surgery. There is a possibility that the growth factors could cause adverse healing of the NVB. There is also a possibility that if residual prostate tissue is present that growth of the tissue could occur. There is a low risk that if the residual prostate tissue were cancerous that the growth factors could contribute to a higher chance of cancer recurrence. The relatively short term effect (<4 hours) of PRP applied topically will significantly decrease the risk of promoting growth of prostate tissue. It is also defined approximately 15-20% of men undergoing radical prostatectomy can expect to have recurrence after surgery. Based on the physiology of growth factors, it is thought the risk of PRP independently increasing risk of prostate cancer recurrence is very unlikely.

Benefits are thought to outweigh the risks of the study. Topical application of autologous PRP at the time of RP will permit supraphysiologic doses of growth factors to be present on the NVB. The growth factors may help promote healing and/or decrease the surgical trauma associated with RP. This may augment healing and recovery of erectile function after RP as measured during the 18 month study duration. Subjects will be asked to complete questionnaires regarding urological symptoms, quality of life (urinary control and ED) before and at 3, 6, 9, 12, and 18 months following the procedure.

2 Study Objectives

Primary Objective: To evaluate the safety and tolerability of using platelet rich plasma on the NVB after nerve-sparing radical prostatectomy.

Secondary Objective(s):

- To assess the feasibility of applying 1 dose of PRP intra-operatively at the time of bilateral nerve-sparing RP in 20 men with prostatic adenocarcinoma.
- To assess preliminary clinical benefit/efficacy of using PRP in facilitating early nerve healing and decreasing ED at 3, 6, 9, 12 and 18 months after nerve-sparing RP. To assess change in urological function by measuring urinary control before and at 3, 6, 9, 12 and 18 months after PRP treatment during nerve sparing surgery.

3 Study Design

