4.4.3 Replacement of Subjects

If subjects withdraw from the study, they will be removed from the final study cohort. In the situation of a subject withdrawing from the study, we will continue to recruit subjects such that 20 total subjects complete the entire study with 18 months of follow-up.

5 Study Drug

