5.4.1 Specifics of PRP Sample Preparation

To prepare the sample, **180** mL of whole blood will be obtained from the patient by venipuncture during the RP by Anesthesia personnel. The whole blood will be placed in the platelet concentration device and centrifuged following manufacturer's instructions. After final processing, the final PRP sample will consist of 10 mL of product that will be used for intraoperative application. The PRP created intra-operatively would be placed into a syringe labeled "PRP." Samples of whole blood and PRP will also be sent to the laboratory for analysis for quality control purposes, in accordance with Division of Laboratory Medicine SOP. ¹⁰

During the RP procedure, PRP will be applied to the NVB after completion of the vesicourethral anastomosis and after conventional techniques have been performed to achieve adequate hemostasis. Conventional techniques for hemostasis include the placement of surgical clips or suture as required to bleeding sites on the neurovascular bundle. No additional hemostatic products will be applied to the neurovascular bundles during the study. PRP will be applied evenly to the entire length of the NVB by mechanical transfer of product. For robotic procedures, a laparoscopic spoon instrument will be used to deliver the PRP directly to the NVB. For open procedures, delivery of PRP will occur via PRP-labelled syringe. After application of PRP, the surgical team will then complete RP in standard fashion.

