7.3 Subject Population(s) for Analysis

Data from all subjects consented for the study and completing postoperative visits will be evaluated.

² Vitals will be abstracted from the medical record for visit 3, post-operative day 2

³ Week 1 and week 12 visits may be done on-site or via telephone interview or email. Physical exam and vitals will be performed for these visits if participant is able to return to Mayo Clinic. Outside records for physical exam and vitals will be requested if visits are done remotely.

⁴ The 6, 9, 12 and 18 Month visits may be done remotely via telephone interview or email. Completed SHIM/EPIC Questionnaires may be returned to study site by mail, email or fax. PSA testing: A local clinic may be used for venipuncture, using mail in lab kit for sample return to Mayo Clinic. PSA testing window for week 12 and 6, 9, 12, 18 month visit is +/- 21d

8 Safety and Adverse Events

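### Men who leave the study after receiving PRP are dropped from the analysis and replaced, so the primary safety analysis can omit adverse events already recorded in treated men

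*Combined protocol and SAP*

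**What the plan says.** The primary objective (section 2, repeated in 3.2) reads: "To evaluate the safety and tolerability of using platelet rich plasma on the NVB after nerve-sparing radical prostatectomy". The product is given once, in theatre (5.4.1): "During the RP procedure, PRP will be applied to the NVB after completion of the vesicourethral anastomosis". A consented man receives it unless the surgical team withdraws him during the operation (4.4.1).

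Three consecutive provisions govern men who leave later:

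- 4.4.1: "Subjects may choose to discontinue study participation after RP surgery and will be counted as withdrawn".
- 4.4.2: "Any collected study data from withdrawn subjects will not be included in the data analysis".
- 4.4.3: "If subjects withdraw from the study, they will be removed from the final study cohort". It adds that "we will continue to recruit subjects such that 20 total subjects complete the entire study with 18 months of follow-up".

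Section 7.3 defines the analysis population: "Data from all subjects consented for the study and completing postoperative visits will be evaluated". No separate safety population of all treated men is defined. The Study Summary, under Statistical Methodology, is broader: "All patients will be evaluated for perioperative complications, length of stay, and need for blood transfusion".

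**The concern.** A man who discontinues after surgery has normally been treated. Under 4.4.2 his data leave the analysis, including adverse events observed and recorded before he left, and another man takes his place. There is no exception for safety data, although safety is the primary objective.

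If leaving is related to complications or poor recovery, reported event rates will be too low and reported recovery too high. If leaving is unrelated, the rate is unbiased, but observed events in treated men still vanish from a summary of about 20 men. Section 1.4 says there are no earlier clinical data for this use, and sections 3.1 and 8.6 compare safety with registry patients. Nothing restricts that comparator to men followed for 18 months, so the two groups could also be selected differently.

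**Working it through.** **Does another section restore the data?**

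- Study Summary: its statement about all patients is general, while 4.4.2 and 4.4.3 deal specifically with withdrawn men. At best the two conflict.
- 7.2 covers missed appointments, where the man is contacted for his data. He is not called withdrawn.
- 7.3 does not say which postoperative visits must be completed. Read as all visits, it repeats a completers-only rule. Read as any visit, it conflicts with 4.4.2 and 4.4.3.
- 8.2 requires all adverse events to be recorded, and 8.6 requires regular review of serious ones. Neither says that withdrawn men are analysed.
- 9.1 keeps the right to use information collected before a man revokes authorization, so privacy rules as the protocol describes them do not force the exclusion.

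None of these overrides 4.4.2.

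**How large could the effect be?** Section 7.1 gives 20 subjects by custom, with no event rate, withdrawal rate or formula, so there is no figure to reproduce. Everything below except the 20 is an assumption.

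Let p = 0.10 be the true proportion of treated men with an event, w0 = 0.05 the withdrawal probability without an event, and we the withdrawal probability after one.

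- Proportion staying: s = p(1 − we) + (1 − p)(1 − w0)
- Reported rate: r = p(1 − we)/s
- Men treated to obtain 20 completers: 20/s
- Expected men with an event who are dropped: (20/s) × p × we
- P(report shows zero) = (1 − r)^20
- P(no event in any treated man) = (0.855/0.955)^20 = 10.9%. Here 0.855 = 0.90 × 0.95 is the probability of staying without an event, and 0.955 = 1 − 0.90 × 0.05 sets aside men who leave without one.
- P(report shows zero but a treated man had an event) = the difference of the last two

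| we | s | Reported rate | Men treated | Event men dropped | P(report zero) | P(false zero) |
|---|---|---|---|---|---|---|
| 0.05 | 0.950 | 0.095/0.950 = 10.0% | 21.1 | 0.11 | 12.2% | 1.2% |
| 0.20 | 0.935 | 0.080/0.935 = 8.6% | 21.4 | 0.43 | 16.7% | 5.8% |
| 0.50 | 0.905 | 0.050/0.905 = 5.5% | 22.1 | 1.11 | 32.1% | 21.1% |

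A simulation of 100,000 trials per row gave 1.2%, 5.8% and 21.0% for the last column.

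**Single cases** (exact 95% intervals)

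- One treated man of 21 has an event and leaves: 0/20 (0 to 16.8%) is reported instead of 1/21 = 4.8% (0.1 to 23.8%).
- Two of 22 do so: 0/20 is reported instead of 2/22 = 9.1% (1.1 to 29.2%).

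**Function.** Assume true recovery of 40%, with 5% withdrawal if recovered and 15% or 30% if not. Reported recovery is 0.38/(0.38 + 0.60 × 0.85) = 42.7% or 0.38/(0.38 + 0.60 × 0.70) = 47.5%. For comparison, 8/20 has an exact 95% interval of 19.1 to 63.9%.

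**The case against.** The strongest counter-argument is that serious events are not hidden from those who must act on them. Under 8.3.1 every serious event goes to the IRB on a worksheet that is also entered in the research database, and under 8.3.2 unexpected serious suspected reactions go to the FDA. Neither duty stops when a man leaves the analysis. This stands: the defect lies in the planned analysis, not in detection or regulatory reporting. It does not put the events back into the analysis.

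Other points stand in part:

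- Withdrawal may be rare. Treatment is a single application, and visits from week 1 can be remote. The 50% scenario has no support in the documents, and with equal 5% withdrawal the effect is small.
- The modelled safety bias also lies within sampling error: 2/20 has an exact 95% interval of 1.2 to 31.7%. The analysis is descriptive, so no test or threshold is affected. The firmer argument is the loss of observed events, not the bias in a rate.
- The exclusion applies to men counted as withdrawn. The sections do not say how men who die or are lost to follow-up are classified, so those men fall under the ambiguous 7.3.
- 4.4.2 says that outcomes remain available, but for use under another protocol. The registry is described as holding oncologic and quality-of-life data, not adverse events.

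**Conclusion.** The concern holds, and the rule must be changed. Followed as written, 4.4.1 to 4.4.3 remove recorded adverse events in treated men from the analysis of the primary objective. That conclusion rests on the text alone and needs no assumed rate.

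The numerical effect is illustrative. It ranges from no bias, when withdrawal is unrelated to events, to roughly half the true rate (5.5% against 10%) in the most adverse scenario shown. The shift in function is smaller than sampling error and is a lesser matter.

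Men withdrawn during the operation (blood loss above 750 mL or advanced disease) are a separate, secondary point. They too are removed and replaced, but no feasibility measure or denominator is defined, so they would be hidden only if feasibility is reported on the final 20. The retained withdrawal reasons and the enrollment log allow the denominator to be recovered. The documents do not say whether the 180 mL draw precedes that decision.

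**What to change.** Reword 4.4.2, 4.4.3 and 7.3 as follows:

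1. The safety analysis includes every man who received PRP, with all data collected up to withdrawal.
2. Function is described in all men given PRP, using all available visits.
3. Replacement may continue, but treated men who are replaced stay in the denominators, and the number treated is reported beside the number completing 18 months.
4. Section 7.3 states which postoperative visits it means, and is made to agree with 4.4.2, 4.4.3 and the Study Summary. It should also say how men who die or are lost to follow-up are handled.

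As a secondary step, report how many consented men went to surgery, how many received PRP and the reasons for non-application. List any adverse events already recorded in men who had the 180 mL draw but no PRP.

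The cost is wording. No new data collection is needed for the period before withdrawal. Events after withdrawal are not clearly collected under the plan, and the fix does not depend on them. Reported rates may look slightly less favourable.
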